9.4 Statistical Analyses

The statistical analysis plan (SAP) will be finalised before the first participant enters the study and it will include a more technical and detailed description of the statistical analyses described in this section. This section is a summary of the planned statistical analyses of the most important endpoints including primary and key secondary endpoints.

Other endpoints as well as demographic, baseline characteristics and disposition will be detailed in the SAP.

Statistical evaluation will be performed using Statistical Analysis System (SAS[®]) Version 9.4 (or higher if available).

9.4.1 General Considerations

9.4.1.1 Reasons for Exclusion from the Analyses

Any major protocol deviation will be described and listed and its impact on inclusion of any participant in each analysis population will be specified. The final list of protocol deviations impacting each analysis population will be reviewed prior to database lock. The list may be updated, up to the point of database lock, to include any additional major protocol deviations impacting inclusion in the PP set.

9.4.1.2 Significance Testing and Estimations

As this is a descriptive safety and efficacy study, no formal statistical testing will be carried out.

9.4.1.3 Statistical/Analytical Methods

Statistical analyses will be performed by an external CRO, managed by the sponsor's Biometry department.

Demographic and Other Baseline Characteristics

Descriptive summary statistics (n, mean, standard deviation (SD), median, minimum, maximum) or frequency counts of demographic and baseline data (medical history, concomitant disease (predosing AEs and ongoing medical history, prior medications and therapies, etc.) will be presented for the FAS, PP and safety sets.

Participant Disposition and Withdrawals

The numbers and percentages of participants screened and included in each of the populations will be tabulated overall and by centre. The reasons for participant exclusions from each of the populations will also be tabulated. Primary reasons for discontinuation of study will be tabulated.

Adjustment for Country/Centre Effects

Descriptive analysis will be carried out to evaluate any possible centre effect.

9.4.2 *Analysis of Primary Endpoints*

The co-primary efficacy variables are

- percentage of participants achieving castrate levels of serum testosterone (<50 ng/dL or 1.735 nmol/L) and
- percentage of participants maintaining the castrate levels from Week 8 to Week 24.

The percentage of participants achieving castrate levels of serum testosterone (<50 ng/dL or 1.735 nmol/L) on Day 29 will be obtained as the number of participants with castrate levels at the visit, divided by the total number of participants on Day 29 in the considered population.

Percentage of participants maintaining the castrate levels of serum testosterone (<50 ng/dL or 1.735 nmol/L) from Week 8 to Week 24 will be calculated as the number of participants with castrate levels at all visits from Week 8 to Week 24, divided by the total number of assessable participants.

To derive the percentage of participants maintaining castration levels of testosterone, missing data will be handled as follows:

- (a) In participants escaping castration at a certain visit, subsequent missing data is irrelevant.
- (b) Participants maintaining castration up to a certain visit with missing data afterwards (drop-out due to non-drug-related reasons) will be excluded from the analysis.
- (c) Participants maintaining castration up to a certain visit with missing data afterwards (drop-out due to drug-related reasons) will be treated as having escaped castration (failure).
- (d) Missing data between two visits where castration levels are maintained will be handled as missing for that particular visit, and the participant will be considered to have maintained castration.

To derive the percentage of participants maintaining castrate levels of testosterone, assessable participants are defined as the total number of all participants having values at all visits and all participants having missing data according to the criteria a), c) and d) mentioned previously. Participants having missing data according to the criteria b) will be excluded from this calculation.

Co-primary endpoints will be tabulated with two-sided 95% (95% CI) using the Clopper-Pearson exact method.

9.4.3 *Analysis of Secondary Endpoints*

9.4.3.1 *Prostate-Specific Antigen*

The secondary efficacy variable is the percent change in PSA from baseline (prior to injection) measured at Week 12 and Week 24. Percent change in PSA is defined as the absolute value of difference between the PSA values at Week 12 and Week 24 and the baseline value divided by the baseline value.

PSA percent change from pre-treatment Day 1 will be reported at each subsequent visit, using descriptive statistics.

9.4.3.2 *Pharmacokinetic and Pharmacodynamic Data Analysis*

Description of Triptorelin and Testosterone Concentrations

Individual plasma or serum concentrations of triptorelin and testosterone will be listed and summarised by visit and time points using descriptive statistics for continuous variables (number of available observations, mean, median, SD, minimum, maximum, geometric mean, and geometric coefficient of variation (assuming log normally distributed data). Data will be

summarised for the PK/PD subset and overall. Individual and mean triptorelin and testosterone concentration time profiles, as well as spaghetti plots, will be generated.

Non-compartmental Analysis

The PK analysis of triptorelin plasma concentrations and testosterone serum concentrations of the rich sampling PK/PD subset will be performed by the non-compartmental analysis (NCA) approach using Phoenix WinNonlin PK program version 8.3 or higher. The following PK parameters will be calculated if warranted by the data:

- maximum observed concentration (C_{\max})
- time to maximum observed blood concentration (t_{\max})
- (for triptorelin only) area under the plasma concentration time curve from time 0 to the time of the last quantifiable concentration (AUC_{last})
- (for triptorelin only) area under the plasma concentration time curve from time 0 to the visit on day 169 (AUC_{0-169})
- (For testosterone only): time to castration t_{castr}

Additional PK parameters may be calculated if appropriate.

Descriptive statistics of PK and PD parameters will be presented for the rich PK analysis set for triptorelin and the rich PD analysis set for testosterone. PK and PD parameters will be summarised by, but not limited to, n, mean, SD, median, minimum, maximum, geometric SD, geometric mean, and geometric coefficient of variation except for t_{\max} where only n, median, minimum and maximum values will be reported.

The NCA analysis will be described in a separate data analysis plan and reported in a standalone report.

Population Pharmacokinetic Analysis

Population pharmacokinetics (PopPK) modelling will be performed using concentrations obtained from all participants in order to describe the pharmacokinetics of triptorelin 6-month formulation in the prostate cancer population (if warranted by the data). In addition, quantification of the inter-participant variability on PK will be performed and an attempt to identify participant characteristics explaining the variability on PK will be made. Historical PK data from other studies may also be used to compare the PK profiles from this study against other populations. The PK model developed will be used to derive exposure metrics to perform an exploratory analysis with efficacy and safety endpoints (should any safety signal emerge). Should a trend be observed, PK/PD modelling will be performed to describe the relationship between exposure and efficacy and/or safety endpoints.

Population PK/PD analysis will be described in a separate data analysis plan and presented in a stand-alone report.

9.4.4 Analysis of Exploratory Endpoint

9.4.4.1 Pharmacokinetic/Pharmacodynamic Relationship

An exploratory analysis will be performed to assess the relationship between PK and PD endpoints. If a trend is shown, an attempt to build a PK/PD model using a population approach will be performed. The PopPK and PK/PD analyses will be described in a separate data analysis plan and reported in a standalone report.

9.4.5 Safety Analyses

Safety endpoints are indicated in Section 3.

All safety data will be included in the participant data listings. Analyses and summary tables will be based upon the safety set.

All AEs will be coded according to the Medical Dictionary for Regulatory Activities (MedDRA) version 24.1 (or higher if available) and will be classified by MedDRA preferred term and system organ class. Adverse event listings will be presented by participant, system organ class and PT.

The incidence of all TEAEs and SAEs will be tabulated overall. In addition, summary tables will be presented by maximum intensity and drug relationship.

A TEAE is defined as any AE that occurs during the active phase of the study (from study intervention injection to 24 weeks after injection) if it was not present prior to receiving study intervention, or:

- it was present prior to receiving IMP but the intensity increased during the active phase of the study.
- It became serious during the active phase of the study
- It was present prior to receiving the study intervention and the intensity was the same, but the causality changed to 'related to treatment' during the active phase of the study.

All TEAEs will be flagged in the AEs listings.

Haematological and biochemical toxicities will be recorded and graded according to the NCI CTCAE criteria, where available. The National Cancer Institute-Common Toxicity Criteria for Adverse Events (NCI-CTCAE) Grade 3 and 4 haematology and biochemistry variables by participant and by cycle will be listed.

Actual values and changes from baseline in clinical laboratory tests, physical examinations, vital signs and 12-lead ECG will be summarized using descriptive statistics at each visit. For laboratory data, abnormal values will be flagged in the data listings and a list of clinically significant abnormal values will be presented. Shift tables using the worst on-treatment grade will be presented for the number and percentage of participants with NCI-CTCAE grades.

AEs reported by investigators using the NCI-CTCAE classification (Version 5.0 or higher) will be coded using MedDRA Version 24.1 (or higher if available).

Summary incidence tables will be provided, classified by SOC, PT and associated NCI/CTC worst grade. In the event of multiple occurrences of the same AEs being reported by the same participant, the maximum intensity (Grade 5 >Grade 4 >Grade 3 >Grade 2 >Grade 1 >missing >not applicable) will be chosen.

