2.6 Change from Statistical Section of the Protocol

Protocol	SAP
Section 9.4.1.3 Demographic and Other Baseline Characteristics Descriptive summary statistics (n, mean, standard deviation (SD), median, minimum, maximum) or frequency counts of demographic and baseline data (medical history, concomitant disease (predosing AEs and ongoing medical history, prior medications and therapies, etc.) will be presented for the FAS, PP and safety sets.	Section 5.5 Medical history, non-drug therapies, medications and surgical procedures will be present for only Safety Set.

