5.8 Safety

5.8.1 *General Consideration*

All safety summaries and analyses will be based upon the Safety Set. All safety data will be included in participant data listings (see listing detail conventions in Appendix A4). This is a single-arm study, and there will be no statistical comparison between the treatment groups for safety data.

Haematological and biochemical toxicities will be recorded and graded according to the National Cancer Institute-Common Toxicity Criteria for Adverse Events (NCI-CTCAE) version 5.0 or higher, where available (refer to appendix A5 for grading using NCI-CTCAE 5.0). The NCI-CTCAE Grade 3 and 4 haematology and biochemistry variables by participant and by visit will be listed.

5.8.2 *Extent of Exposure*

Summary of the actual dose and duration of exposure will be provided on the Safety Set. Actual dose will be calculated as planned dose (22.5 mg) multiplied by (1 - percentage of residual in syringe). The definition of the duration of exposure is from first IMP administration to the date of end of study. Participant's exposure data will be listed on the Safety Set.

5.8.3 *Adverse Event*

All adverse events (AEs) recorded in the eCRF will be coded using the latest version of MedDRA dictionary in effect within IPSEN at the time of the database lock. AEs will be classified as Treatment-Emergent AEs (TEAEs) according to the rules below:

- Events with start date on or after the date of IMP administration and up to 24 weeks after date of first dose of treatment.
- Events whose severity (measured by National Cancer Institute – Common Toxicity Criteria (NCI-CTCAE) Version 5.0 grading) worsens on or after the date of IMP administration,

Refer to appendix ‘

[Partial/Missing Date Convention](#)’ for handling of partial date.

In the case where it is not possible to define an AE as treatment emergent or not, the AE will be classified by the most conservative case; i.e. treatment emergent.

In addition, if severity of an AE changes during the study, a separate AE will be recorded for each severity on the AE eCRF. The “first” and subsequent AEs will be identified based on the AE start date or the severity change date. If “first” AE record occurs before dosing, and subsequent AEs occur on or after dosing, subsequent AEs whose severity worsens compared with the severity of “first” AE record will be classified as TEAE. If “first” AE record occurs on or after dosing, “first” AE record and subsequent AEs will be classified as TEAE.

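### For adverse events already present before dosing and not worsening in grade, the SAP omits two of the protocol's treatment-emergent criteria and does not declare the change

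*Protocol*

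**What the plan says.** Protocol 9.4.5 starts from a general rule: "A TEAE is defined as any AE that occurs during the active phase of the study", where the active phase runs from the injection to 24 weeks later and the event was not present beforehand. It then adds three routes:

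- **Intensity:** "it was present prior to receiving IMP but the intensity increased during the active phase of the study".
- **Seriousness:** "It became serious during the active phase of the study".
- **Causality:** for an event present before dosing, "the intensity was the same, but the causality changed to 'related to treatment' during the active phase of the study".

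SAP 5.8.3 gives two rules:

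- **Onset:** "Events with start date on or after the date of IMP administration and up to 24 weeks after date of first dose of treatment".
- **Worsening:** an event also counts when its CTCAE severity "worsens on or after the date of IMP administration".

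For an AE first recorded before dosing, the SAP repeats that later records become TEAEs when severity is worse than in the first record. It describes opening a separate AE record only when severity changes. Where treatment-emergent status cannot be determined, the event is classed as treatment-emergent.

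SAP 2.6, which tabulates changes from the protocol's statistical section, has a single entry. It concerns the analysis set for medical history and therapies: "surgical procedures will be present for only Safety Set". The TEAE definition is not mentioned.

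**The concern.** Incidence of TEAEs up to Week 24 is the first secondary endpoint in the protocol's table of objectives and endpoints. The study is single-arm and descriptive, so the TEAE counts are themselves the safety result, with no comparison against which a small difference in definition would cancel. Protocol 9.4 presents the SAP as a more detailed account of the same analyses. Removing two routes into the endpoint changes its definition, and a programmer following SAP 5.8.3 would not produce the endpoint the protocol describes. The events concerned are few, but each one either became serious or was attributed to the drug after dosing.

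**Working it through.** No figure in the plan needs reproducing, because the point rests on comparing two definitions. The inputs are Protocol 9.4.5 and SAP 5.8.3, with SAP 2.6 checked for a declared change.

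**Step 1. Classify each type of event under both texts.**

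| Type | Event | Protocol 9.4.5 | SAP 5.8.3 |
|---|---|---|---|
| A | Starts after dosing, within 24 weeks; later serious or related | TEAE | TEAE (onset rule) |
| B | Present before dosing; grade rises within 24 weeks after dosing | TEAE | TEAE (worsening rule) |
| C | Present before dosing; grade does not worsen; becomes serious in the active phase | TEAE | Not a TEAE |
| D | Present before dosing; same grade; causality changes to related in the active phase | TEAE | Not a TEAE |

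The definitions part company in types C and D only.

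**Step 2. Can types C and D occur?** Yes. Protocol 8.4.1 records AEs from consent, and screening runs from Day -28 to Day -1, so there are up to 28 days in which such an event can begin. Protocol 10.3.3 separates seriousness from severity, and hospitalisation alone makes an event serious under 10.3.2, so type C needs no change of grade. Protocol 10.3.3 also lets the investigator revise a causality judgement as follow-up information arrives, so type D is possible.

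**Step 3. Does anything else in the SAP bring them back?** No. The conservative default applies only when status cannot be determined. For types C and D the SAP rules give a definite answer, which is that the event is not treatment-emergent.

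**Step 4. Where would these events still be seen?** According to the list of outputs in SAP 5.8.3:

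- Type C is absent from the TEAE tables and the treatment-emergent SAE table. It is present in the SAE tables that are not restricted to treatment-emergent events (by SOC and PT, by maximum grade, by maximum causality), in the treatment-related SAE table if judged related, and in the SAE listing.
- Type D, if non-serious, is absent from the TEAE tables, including those for treatment-related TEAEs and for TEAEs by causality. The SAE tables do not apply to it. It remains in the any-AE row of the overview and in the all-AE listing, flagged as not treatment-emergent.

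**Step 5. The 24-week limit.** The SAP's worsening rule states no end point, whereas the protocol confines worsening to the active phase. Twenty-four weeks is 24 × 7 = 168 days, and Day 1 + 168 = Day 169, the day of the last scheduled visit. With the ±3-day window that visit falls no later than Day 172. For a participant on schedule the two texts can therefore differ over at most 3 days.

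**The case against.** A reader might infer that any event turning serious or drug-related after dosing is lost from the TEAE counts. The documents do not support that. The SAP's onset rule captures every AE starting from dosing to 24 weeks, whatever its later seriousness or causality.

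A reader might also infer that serious events disappear from the safety report. They do not, because the all-SAE tables and listing are independent of treatment-emergent status.

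The gap is narrower still for two reasons. Under Protocol 10.3.3, Grade 4 is life-threatening and Grade 5 is death, so a lower-grade event that becomes life-threatening or fatal must rise in grade and is caught by the worsening rule. What remains under type C is mainly hospitalisation, disability or other medically important seriousness at an unchanged grade. Type D requires an event that began before the single injection to be attributed to that injection later, without any change in grade, and this may never happen.

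The missing 24-week limit can only add events, and only over a few days.

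All of this stands, and it limits the size of the problem. It does not remove the mismatch: the two documents define a named secondary endpoint differently, and the section meant to list such differences is silent.

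**Conclusion.** The inconsistency is real and confined to AEs present before dosing whose CTCAE grade does not worsen. For these, TEAE and treatment-emergent SAE counts under the SAP can fall below the protocol-defined counts. The non-serious event re-judged as related is the one that matters most for reporting, because no treatment-related table shows it.

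The number affected is probably small and could be zero. That judgement rests on the short period in which such events can start and on the assumption that many events becoming serious also rise in grade. The documents give no rate of AEs during screening, so no estimate is possible. The co-primary efficacy endpoints are untouched. The 24-week difference is a minor matter of consistency. The point merits a correction before the safety tables are programmed, mainly so that the study report does not carry two definitions of the same endpoint.

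**What to change.** Add the protocol's seriousness and causality criteria to the TEAE derivation in SAP 5.8.3. As a minor edit in the same place, limit the worsening rule to the protocol's 24-week active phase.

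The text change is a few lines. The real work is checking the data: the SAP describes a new record only for a severity change, so confirm that the timing of a change in seriousness or causality can be derived from the AE and SAE records. Where that timing is unknown, treat the event as treatment-emergent, in keeping with the SAP's own conservative default.

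If the sponsor intends the narrower definition, declare and justify it in SAP 2.6 instead. That costs one table row and no programming.

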9.4.6 Subgroups Analyses

No subgroups analysis will be performed.

9.4.7 Other Analyses

Not applicable.

9.5 Interim Analyses

No interim analysis will be performed.

10 SUPPORTING DOCUMENTATION AND OPERATIONAL CONSIDERATIONS

10.1 Appendix: Regulatory, Ethical, and Study Oversight Considerations

10.1.1 *Regulatory and Ethical Considerations*

- This study will be conducted in accordance with the protocol and with the following:
 - Consensus ethical principles derived from international guidelines including the Declaration of Helsinki and Council for International Organisations of Medical Sciences International Ethical Guidelines
 - International Council for Harmonisation (ICH) Good Clinical Practice (GCP) Guidelines
 - Applicable laws and regulations such as Regulation EU 536/2014
- The protocol, protocol amendments, ICF, Investigator Brochure, and other relevant documents (e.g. any participant recruitment materials) must be approved by the IRB/IEC before the study is initiated.
- Any amendments to the protocol will require IRB/IEC approval before implementation of changes made to the study design, except for changes necessary to eliminate an immediate hazard to study participants.
- The protocol and any substantial amendments to the protocol will require health authority approval prior to initiation except for changes necessary to eliminate an immediate hazard to study participants.
- The investigator will be responsible for the following:
 - Providing written summaries of the status of the study to the IRB/IEC annually or more frequently in accordance with the requirements, policies, and procedures established by the IRB/IEC
 - Notifying the IRB/IEC of SAEs or other significant safety findings as required by IRB/IEC procedures
 - Providing oversight of the conduct of the study at the site and adherence to applicable local regulations, ICH guidelines and the IRB/IEC requirements/procedures.

10.1.2 *Financial Disclosure*

Investigators and sub-investigators will provide the sponsor with sufficient, accurate financial information as requested to allow the sponsor to submit complete and accurate financial certification or disclosure statements to the appropriate regulatory authorities. Investigators are responsible for providing information on financial interests during the course of the study and for one year after completion of the study.

10.1.3 *Informed Consent Process*

- The ICF and any participant recruitment materials must be in compliance with ICH GCP, local regulatory requirements, and legal requirements, including applicable privacy laws. They must be approved prior to use as described in Section 10.1.1.
- The investigator or his/her authorised representative will explain to the participant or their legally authorised representative the nature and objectives of the study and possible risks and benefits associated with the participation. They will answer all questions regarding the study.

- Participants or their legally authorised representative, when applicable must be informed that their participation is voluntary.
- The investigator or his/her authorised representative will obtain written informed consent from each participant or the legally authorised representative, when applicable, before any study-specific procedure is performed. The investigator will retain the original of each participant's signed ICF.
- A copy of the signed ICF(s) must be provided to the participant or their legally authorised representative.
- The medical record must include a statement that written informed consent was obtained before the participant was enrolled in the study and the date the written consent was obtained. The authorised person obtaining the informed consent must also sign the ICF.
- Participants must be re-consented to the most current version of the ICF(s) during their participation in the study. If changes to the ICF do not apply to all participants, this will be communicated to the IRB/IEC with a rationale. IRB/IEC approval must be received before implementation as required by local regulations.
- The ICF will contain a separate section that addresses the use of all data combined with data from prostate cancer patients from other parts of the world. These data may only be used for analysis to advance science and public health, including in order to:
 - understand and evaluate the study drug and/or other drugs,
 - better understand the studied disease and associated health problems,
 - develop new drugs and find new ways to detect, treat, prevent or cure health problems,
 - plan new studies or improve scientific analysis methods,
 - publish research results in scientific journals or use them for educational purposes,
 - conduct additional statistical analysis.
- Participants will be told that they are free to refuse to participate and may withdraw their consent at any time and for any reason during the study.
- If a pregnancy is reported for a female partner of a male participant during the study, the partner will be asked to sign appropriate consent for the sponsor to follow the outcome of the pregnancy.

